9.7 Statistical Methods Planned in the Protocol and Determination of Sample Size

9.7.1 Statistical and Analytical Plans

This section presents statistical methods used in the analyses as described in the final statistical analysis plan (SAP) dated 30 November 2015 and an SAP addendum dated 06 April 2016. Both documents were prepared by [REDACTED] and approved by the Sponsor before final database lock. Changes from analyses planned in the protocol are listed separately in Section 9.8.2.

Subsequent to the approval of the SAP Addendum, a few items received further clarification or adjustment:

- Subjects who were intubated and/or heavily sedated at Baseline were eligible for the study, but were not considered fully evaluable on the GCS.
- It was stated that the modified Intent-to-Treat (mITT) Analysis Set should contain all Intent-to-Treat (ITT) subjects who were fully evaluable on the GCS at Baseline and who had at least 1 post-Baseline GCS assessment in the interval from 0 through 90 minutes post-randomization. Although the description of this analysis set changed after database lock, none of the subjects included/excluded in this set changed as a result.

- The final analyses did not treat GCS scores of 2 as ‘missing’ (as specified in the SAP Addendum), but reverted to the original planned handling to ensure that any potential post-Baseline deterioration of subjects would be captured.

9.7.1.1 General Considerations

Baseline core body temperature was the first rectal temperature $\geq 40.0^{\circ}\text{C}$ taken during the Screening period.

The main focus of all efficacy analyses was to describe the course of subject recovery during the study and to obtain estimates of the treatment effect. In general, all efficacy and safety variables were summarized using descriptive statistics. Continuous variables were summarized by descriptive statistics (sample size [n], mean, standard deviation [SD], 2-sided 95% confidence interval [CI] around the mean; median, minimum, and maximum).

Categorical variables and binomials (such as occurrence of events) were summarized in frequency tables which display the number and percentage of subjects reporting a particular response or outcome. All observed significance levels (“p-values”) that were reported were from 2-sided statistical tests unless otherwise specified, and were regarded as exploratory. Individual subject data were presented in listings.

All analyses, summaries, and listings were generated using SAS[®] version 9.4 or later.

9.7.1.2 Data to be Analyzed

Data to be analyzed were collected using Inform version 5.5. Data handling was the responsibility of [REDACTED] The data were inspected for inconsistencies by performing validation checks. All data collected during the study were reported.

9.7.1.3 Analysis Sets

The Enrolled Analysis Set included:

- Subjects who gave informed consent prior to participation.
- Subjects whose family member or authorized representative gave informed consent for the subject prior to participation.
- Subjects who entered the study under a waiver of informed consent.

Waiver of a subject’s informed consent occurred in the event the subject was unable to consent due to his/her medical status and a family member or authorized representative was not available at the time of hospital admission.

Once the study subject was capable of providing his/her own informed consent, then the subject was re-consented. If the subject was unwilling to provide consent at that time, the

subject was withdrawn from the study; and no further study procedures or testing were performed.

The Randomized Analysis Set contained all enrolled subjects who were randomized. For analyses and displays based on the Randomized Analysis Set, subjects were classified according to randomized treatment.

All efficacy was analyzed by planned treatment arm. Classification of subjects with respect to the ITT, [REDACTED] and Safety Analysis Sets was conducted prior to the final database lock.

9.7.1.4 *Missing Data*

Imputation of data in the mixed-model repeat measure (MMRM) analyses was not required, as the MMRM method provided appropriate weighting of the sample means based on the amount of data that each subject contributes.

Imputation of data was not required for any time-to-event analysis. Subjects were censored at the earlier of the 72 hours or discontinuation from the study.

Imputation of missing data was done on cooling rate (based on rectal temperature), using straight-line interpolation for non-monotonically missing data points only.

All other efficacy analyses methods consisted of descriptive statistics for observed cases.

9.7.1.5 *Adjustments for Covariates and Factors to be Included in Analyses*

Analysis of covariance (ANCOVA) models, including repeated-measure ANCOVA models, included the subject's respective Baseline value as a covariate.

Study site (location) was originally planned as a stratification factor in various analyses.

Study sites were [REDACTED]

[REDACTED] The specific analysis sections of the original SAP described how study site was to be used in the models (where applicable). Due to the actual study size, study site was deleted from all models and no tables or figures by study site were produced.

9.7.1.6 *Multicenter Studies*

This study was conducted at a single main site [REDACTED] and [REDACTED] satellite site locations [REDACTED].

[REDACTED] Randomization to treatment arms was stratified by study site. All data were pooled for analyses. A term for treatment-by-center (study site) interaction was not included in the primary analysis model, but the presence of such an interaction was explored via graphical methods (e.g., Forest plots) to assess whether the interaction was quantitative (i.e., the treatment effect was consistent in direction but not size of effect) or qualitative (i.e., the treatment was beneficial at some but not other treatment locations).

9.7.1.7 *Subject Disposition*

The disposition summary included all subjects. The summary included the number and percentage of subjects who were screened, enrolled, screen-failed (with reasons for failure), were randomized, were treated, completed the study, or discontinued prematurely, along with

the primary reason for discontinuation. The informed consent status and (where applicable) the reasons why informed consent was not obtained were also presented. The summary was presented by treatment arm.

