9.7.1.10.1 Adverse Events

Adverse events were coded using the Medical Dictionary for Regulatory Activities (MedDRA) version 17.1. For each study treatment, numbers of events and incidence rates were tabulated by preferred term and system organ class. For each subject, an event that occurred one or more times after randomization contributed one observation to the numerator of the incidence rate. The denominator of the rate comprised all randomized subjects who received any treatment (i.e., the Safety Analysis Set). If the severity or seriousness of the AE changed, the overall severity or seriousness were the maximum severity or seriousness of the multiple occurrences.

Adverse events were listed for each subject and summarized by MedDRA system organ class and preferred term.

For this study, “treatment-emergent” AEs (TEAEs) were defined as AEs that started or worsened in severity on or after the initiation of first administered study treatment (SOC and Ryanodex, or SOC only). The incidence of all TEAEs, SAEs, related AEs, and related SAEs, was tabulated by treatment arm, overall and by maximum intensity. AEs leading to death, and AEs leading to withdrawal of subjects also were tabulated for each treatment group. Deaths due to any cause during the study were tabulated by treatment arm. Cases of rhabdomyolysis and ARF were identified at Baseline; any new cases that were identified post-Baseline or which worsened after the Baseline were reported as AEs. Post-Baseline severe respiratory distress or other medically important emergent events were reported as AEs. However, only AEs which occurred or worsened on or after the initiation of first administered study treatment were tabulated as TEAEs.

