
 • A greater proportion of subjects treated with SOC and Ryanodex exhibited a clinically meaningful improvement in their neurological functioning (GCS ≥ 13) within 90 minutes (29.4%) and within 24 hours post-randomization (47.1%), compared to SOC only-treated subjects (11.8% and 23.5%, respectively) (ITT Analysis Set). • A greater proportion of subjects treated with SOC and Ryanodex achieved a clinically meaningful improvement (GCS score ≥ 13) in their neurological functioning as early as 45 minutes post-randomization compared to subjects treated with SOC only, and that difference in favor of the SOC and Ryanodex group remained unchanged at the end of the Treatment Phase (2 hours post-randomization) (ITT and mITT Analysis Sets). • The odds of achieving a GCS score ≥ 13 within 90 minutes post-randomization was about 3 times greater for subjects in the SOC and Ryanodex group than for subjects who received SOC only, and remained almost unchanged at or prior to 24 hours post-randomization (ITT Analysis Set). • Among fully evaluable subjects at Baseline, the odds of achieving a GCS score ≥ 13 within 90 minutes post-randomization was about 6 times greater in the SOC and Ryanodex group than for subjects who received SOC only (mITT Analysis Set). • Among fully evaluable subjects at Baseline, the mean change from Baseline in GCS score was higher in the SOC and Ryanodex group (3.1; $p=0.017$) compared with the SOC only group (1.1; $p=0.179$); the mean percent change from Baseline in GCS score was also higher in the SOC and Ryanodex group (55.6%; $p=0.073$) compared with the SOC only group (20.2%; $p=0.212$). In both cases, the within-group p-value clearly favors the SOC and Ryanodex group, compared with the SOC only group (mITT Analysis Set). • The proportion of subjects who achieved complete normalization in their level of consciousness (GCS score = 15) was greatest at 24 hours post-randomization and was greatest in the SOC and Ryanodex group (41.2%) than in the SOC only group (23.5%) (ITT Analysis Set). • Duration of SOC was substantially shorter in the SOC and Ryanodex group compared to the SOC only group (ITT Analysis Set). • The time to reach first rectal temperature $\leq 38^{\circ}\text{C}$ was similar in both treatment groups (ITT Analysis Set). • The median time to reach first rectal temperature $\leq 38^{\circ}\text{C}$ was shorter in the SOC and Ryanodex group (90.0 minutes) than in the SOC only group (103.0 minutes). In addition, the time at which at least 75% of the subjects had first rectal temperature $\leq 38^{\circ}\text{C}$ was also shorter in the SOC and Ryanodex group (125.0 minutes) than in the SOC only group (195.0 minutes) (mITT Analysis Set). • Overall mean cooling rates were similar in both treatment groups (ITT and mITT Analysis Sets). 
Subjects treated with Ryanodex in addition to SOC, exhibited greater clinically meaningful improvement in their neurological functioning compared to SOC only-treated subjects. The observed incremental improvement in neurologic functioning constitutes a clinically relevant benefit, known to be associated
		

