
Name of Sponsor/Company: Eagle Pharmaceuticals, Inc.	Individual Study Table	(For National Authority Use only)
Name of Finished Product: Ryanodex® (dantrolene sodium) for injectable suspension		
Name of Active Ingredient: Dantrolene sodium		
with lower risk of EHS-related complications, and decreased long-term morbidity and mortality.		

Safety Results:
 
 • Ryanodex was safe and well-tolerated by subjects in the SOC and Ryanodex group. • No new and/or unexpected safety signals were detected. • The overall incidence of TEAEs was similar in both groups. • No treatment-related TEAEs were reported. • No subjects withdrew due to TEAEs. • There were no clinically meaningful differences in laboratory abnormalities between the two treatment groups. • There were no clinically meaningful differences in vital signs, ECGs, ETCO₂, or oxygen saturation between the two treatment groups. • The safety profile of Ryanodex in this study population was consistent with the known and well-characterized safety profile in the currently approved indications. 		

Conclusion:
 
Overall, Ryanodex administered to EHS subjects was safe and well tolerated. The safety profile of Ryanodex in this severely ill population was consistent with its known and well-characterized safety profile in the currently approved indications.
 
Subjects treated with Ryanodex, in addition to SOC, exhibited greater clinically meaningful improvement in their neurological functioning compared to SOC only-treated subjects. The observed incremental improvement in neurologic functioning constitutes a clinically relevant benefit, known to be associated with lower risk of EHS-related complications, and decreased long-term morbidity and mortality.
 
The results of the study provide clinical evidence of the therapeutic benefit that Ryanodex may deliver to patients with EHS.

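### The readable censoring rule makes no exception for death, so a Kaplan-Meier curve of time to rectal temperature ≤ 38°C would run too high in any arm where a death precedes cooling

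*SAP*

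**What the plan says.** SAP 9.7.1.4 (Missing Data) covers time-to-event endpoints in two sentences: "Imputation of data was not required for any time-to-event analysis", followed by "Subjects were censored at the earlier of the 72 hours or discontinuation from the study". Neither mentions death or a competing event.

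SAP 9.7.1.7 (Subject Disposition) gives treated subjects two end states: "completed the study, or discontinued prematurely". A subject who dies during the study did not complete it, so discontinuation is the natural class. Deaths otherwise appear as a safety item in SAP 9.7.1.10.1: "Deaths due to any cause during the study were tabulated by treatment arm".

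The readable result that depends on the rule is time to first rectal temperature ≤ 38°C (Synopsis, Efficacy Results). For the mITT set the synopsis gives medians of 90.0 minutes (SOC and Ryanodex) and 103.0 minutes (SOC only). It also gives "the time at which at least 75% of the subjects had first rectal temperature" at or below that level, which is 125.0 and 195.0 minutes. For the ITT set it says only that the arms were similar. P-values are exploratory (SAP 9.7.1.1).

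**The concern.** Censoring assumes that a subject who leaves observation could still have the event later. A subject who has died cannot. Kaplan-Meier passes that subject's weight to those still at risk, so the estimated share cooled is too high from the next cooling event onward, and quantile times read from the curve can be too early.

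At stake are the level of each arm's cooling curve and the published median and 75% times. The primary endpoint, GCS ≥ 13 by 90 minutes, and the cumulative GCS percentages are counts over subjects and do not use this rule.

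**Working it through.** **Inputs**
- Censoring rule: SAP 9.7.1.4.
- Cooling times (mITT): 90.0 and 125.0 minutes against 103.0 and 195.0 minutes, from the Synopsis.
- ITT arm size: 34 subjects were randomized. The ITT percentages 29.4 and 47.1 are 5/17 and 8/17; 11.8 and 23.5 are 2/17 and 4/17. So there are 17 per arm.
- mITT arm size: not readable. I use 10 as an illustration.
- Deaths: number and timing not readable. Every death pattern below is assumed.

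The published times cannot be reproduced without subject-level data.

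**Formula.** Let n be the arm size, k the number cooled so far, and d the number who died before cooling so far. With no other earlier censoring, the Aalen-Johansen cumulative incidence is k/n. One minus Kaplan-Meier is F = 1 − ∏(1 − 1/r), taken over cooling events, with r the number at risk. If the deaths come before any cooling, F = k/(n − d), and

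excess = k/(n − d) − k/n = F × d/n.

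For any other order the excess is at most F × d/n. Listing every order with one or two deaths, for n = 17 and n = 10, gave no exception.

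**Quantile times, n = 17, one death before any cooling.** The Kaplan-Meier curve reaches 50% at the 8th cooling (8/16 = 50.0%); the cumulative incidence does so at the 9th (9/17 = 52.9%). For 75% it is the 12th (12/16 = 75.0%) against the 13th (13/17 = 76.5%). Each time is thus one cooling event too early. With the death placed after 4, 8, 10, 12, 15 or 16 coolings, neither time shifts.

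**Excess at the first step at or above 75%, deaths before any cooling**

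| n | d | Kaplan-Meier reads | Cumulative incidence | Excess (points) |
|---|---|---|---|---|
| 17 | 1 | 12/16 = 75.0% | 12/17 = 70.6% | 4.4 |
| 17 | 2 | 12/15 = 80.0% | 12/17 = 70.6% | 9.4 |
| 10 | 1 | 7/9 = 77.8% | 7/10 = 70.0% | 7.8 |
| 10 | 2 | 6/8 = 75.0% | 6/10 = 60.0% | 15.0 |

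In two of these rows another order of events gives more, because the first step past 75% then reads higher:
- n = 17, d = 1: one subject cools, one dies, then 12 of the remaining 15 cool. F = 1 − (16/17)(3/15) = 81.2%, against 13/17 = 76.5%; the excess is 4.7 points.
- n = 10, d = 2: six cool, one dies, one cools, one dies, the last cools. F = 100%, against 8/10 = 80%; the excess is 20.0 points.

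**Comparison between arms (assumed scenario).** Cooling times are lognormal, matched to the mITT quantiles (log-SD 0.487 and 0.946), with 17 per arm. Deaths are uniform over 0.5–3 h and independent of cooling time.
- Two deaths in each arm, 75% times: 124 instead of 127 min (SOC and Ryanodex) and 195 instead of 205 min (SOC only). The gap is 195 − 124 = 71 min under Kaplan-Meier and 205 − 127 = 78 min corrected, so it narrows.
- Same deaths, percent cooled: the gap is about 17 points under Kaplan-Meier against 16 corrected at 125 min, so it widens. With d deaths first in each arm, the gap is (k₁ − k₂)/(n − d) instead of (k₁ − k₂)/n, where k₁ and k₂ are the numbers cooled in the two arms.
- Two deaths in SOC only and none in the other arm: gap in 75% time 73 against 83 min. Two in the Ryanodex arm and none in SOC only: 60 against 57 min.

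Spread over 0.5–24 h instead, six deaths per arm of 17 add only 0.9 and 1.0 points, because most subjects cool first.

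**The case against.** The endpoint methods are largely redacted and Kaplan-Meier is not named in the readable text, so a separate death rule may exist. The documents never say that death counts as discontinuation. SAP 9.7.1.10.1 tabulates AEs leading to death apart from AEs leading to withdrawal. If death is not discontinuation, the printed rule censors the subject at 72 hours, which is what the correction would do when there are no other losses. All of this stands: the text leaves room for a wrong curve but does not prove one.

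The exposure is also narrow. By the reported mITT times, at least 75% had cooled by 125 and 195 minutes, so a death must come early to matter. On the subjects excluded from the mITT set, the SAP (9.7.1) says: "Subjects who were intubated and/or heavily sedated at Baseline were eligible for the study, but were not considered fully evaluable on the GCS". Early deaths may therefore be rarer in that set. The scenarios pair mITT quantiles with the ITT arm size, so they are illustrations only.

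The Synopsis adds "No subjects withdrew due to TEAEs". That does not settle the matter. It gives no death count, and SAP 9.7.1.3 provides for withdrawal when re-consent is refused, so losses other than death are possible.

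A reader might infer that the published cooling times are wrong, or that the rule favours Ryanodex. The documents support neither. No death before cooling is shown, and with equal early deaths the gap between arms narrows on one scale and widens on the other.

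**Conclusion.** The concern holds as a minor point, with medium confidence. It rests on three assumptions: death is handled as discontinuation, the estimator is Kaplan-Meier, and no redacted rule overrides 9.7.1.4. Under these, each arm's curve is at or above the true cumulative incidence, by at most F × d/n when there is no other earlier censoring. The excess stays below one subject's share per death until the curve nears 100% (1/17 = 5.9 points, or 1/10 = 10 points for the illustrative arm). The actual error is unknown and may be zero. The direction of any effect on the treatment comparison is not fixed.

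**What to change.** For time-to-event endpoints, treat death before the event as a competing event and report the Aalen-Johansen cumulative incidence. Censor only other losses, including withdrawal at re-consent, at discontinuation. When there are no other losses before 72 hours, this is the same curve as keeping deaths event-free to 72 hours.

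Beside each curve, give the number of deaths before the event by arm. If there were none, one sentence saying so closes the question and the curves stand.

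Section 9.7 describes completed analyses, so the cost is a clarification and, if any such death occurred, a small rerun with a recode of status and time. Deaths and reasons for discontinuation are already tabulated by arm; the recode also needs the time of each death. The drawback is that the curves may look slightly less favourable.

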Test Product, Dose and Mode of Administration, Batch Number: Ryanodex (dantrolene sodium) for injectable suspension; 250 mg/vial to be reconstituted with 5 mL of sterile water for injection (without a bacteriostatic agent) to yield a 50 mg/mL suspension; administered as a rapid IV push of 2.0 mg/kg or 1.0 mg/kg. Batch numbers of Ryanodex and sterile water for injection were [REDACTED] and [REDACTED], respectively.		
Duration of Treatment: Up to 72 hours, from Screening to medical discharge from the study.		
Reference Therapy: Standard of Care (SOC): All subjects in both treatment groups received SOC (efficient cooling and supportive measures).		
Criteria for Evaluation: Efficacy: The primary efficacy endpoint was cumulative incidence of subjects who had achieved a GCS score ≥ 13 at or prior to 90 minutes post-randomization. Secondary efficacy endpoints consisted of the following: 
 • Cumulative incidence of subjects who had achieved a GCS score ≥ 13 at planned time points • Changes from Baseline, and percent changes from Baseline in GCS scores over time • [REDACTED] • [REDACTED] 		

Name of Sponsor/Company: Eagle Pharmaceuticals, Inc.	Individual Study Table	(For National Authority Use only)
Name of Finished Product: Ryanodex® (dantrolene sodium) for injectable suspension		
Name of Active Ingredient: Dantrolene sodium		

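### Event-free subjects are censored at 72 hours or discontinuation rather than at their last reading, so the time to rectal temperature ≤ 38°C can be overstated

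*SAP*

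**What the plan says.** SAP section 9.7.1.4 (Missing Data) gives one rule for all time-to-event analyses. It states "Imputation of data was not required for any time-to-event analysis" and continues: "Subjects were censored at the earlier of the 72 hours or discontinuation from the study". The last assessment of the outcome is not mentioned.

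Three other places bear on the rule:

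- The Synopsis gives the duration of treatment as "Up to 72 hours, from Screening to medical discharge from the study", so observation can end before 72 hours.
- SAP section 9.7.1.7 lists subjects who "completed the study, or discontinued prematurely" as separate disposition categories. The visible text does not say whether medical discharge before 72 hours counts as discontinuation for censoring.
- SAP section 9.7.1.3 says that someone who regains capacity and refuses consent leaves the study: "subject was withdrawn from the study; and no further study procedures or testing were performed".

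The Synopsis (Efficacy Results) reports, for the mITT set, median times to first rectal temperature ≤ 38°C of 90.0 minutes (SOC and Ryanodex) and 103.0 minutes (SOC only). It adds that the 75% time "was also shorter in the SOC and Ryanodex group (125.0 minutes) than in the SOC only group (195.0 minutes"). For the ITT set it calls the time to ≤ 38°C similar in the two groups.

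**The concern.** A subject is known to be above 38°C only up to the last reading above 38°C. After that the status is unknown. Standard practice is to remove such a subject from the risk set at the last assessment. The stated rule keeps the subject at risk, as event-free, until discontinuation or 72 hours.

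The upper percentiles of a small arm are the figures most exposed to this. The 75% time, with a reported gap of 195.0 − 125.0 = 70 minutes, is presented as a result favouring Ryanodex. SAP section 9.7.1.1 makes estimation of the treatment effect a main aim of the efficacy analyses, so a rule that can push an estimate in one direction matters even when p-values are only exploratory.

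**Working it through.** **Plan's own figures.** The times 90.0 (125.0) and 103.0 (195.0) minutes cannot be reproduced. The documents give no subject-level times, event counts, numbers censored, reading schedule or mITT arm sizes. Seventeen per ITT arm is inferred from the reported percentages: 5/17 = 29.4% and 2/17 = 11.8%, with 34 randomized. The estimator is not named in the visible text; Kaplan-Meier is assumed.

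**Direction.** The Kaplan-Meier event-free curve is S(t) = ∏(1 − d/r) over event times up to t, where d is the number of events and r the number at risk. Moving a censoring time later can only raise r at later events. Each factor then rises or stays the same, and so does S(t), so every percentile is the same or longer.

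**Which subjects can matter.** S(t) uses risk sets only up to t, so a subject censored after a percentile is reached cannot change it. For the 75% times, only event-free subjects whose readings stopped before 195.0 minutes (SOC only) or 125.0 minutes (SOC and Ryanodex) matter. For the medians, the limits are 103.0 and 90.0 minutes. If they were all carried past those times, the 75% time can be reached only if they are at most 25% of the arm: 4 of 17, or 2 of 11 or of 8.

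**Illustration 1: 17 per arm, times fitted to each arm's reported figures.** Lognormal, σ = ln(75% time / median)/0.6745. This gives ln(195/103)/0.6745 = 0.946 for SOC only and ln(125/90)/0.6745 = 0.487 for SOC and Ryanodex. Event i is placed at quantile (i − 0.5)/17, and the last k subjects have no event.

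Worked case, SOC only, k = 2:

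- 72-hour rule: S after j events is 1 − j/17, first ≤ 0.25 at j = 13 (4/17 = 0.235), at 187 minutes.
- Last reading at 90 minutes: 8 events come first (S = 9/17), leaving 17 − 8 − 2 = 7 at risk. After 4 more events S = 9/17 × 3/7 = 0.227, at 159 minutes. The shift is 187 − 159 = 28 minutes.

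| Assumed last reading | k | SOC and Ryanodex, 75% time | SOC only, 75% time | Medians |
|---|---|---|---|---|
| none event-free | 0 | 122, no change | 187, no change | no change |
| 200 minutes or later | 1 to 4 | no change | no change | no change |
| 90 minutes | 1 to 4 | 122 to between 104 and 122 | 187 to between 137 and 187 | no change |
| 1 minute (extreme) | 4 | 122 to 97 | 187 to 118 | 90 to 78; 103 to 78 |

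**Illustration 2: simulation over arm sizes.** Assumptions: lognormal crossing times with median 85 and 75% time 130 minutes (σ = ln(130/85)/0.6745 = 0.630). In m subjects of an arm, readings stop at a uniformly drawn 30% to 100% of their own crossing time. There are 3,000 runs per cell. Entries are typical (median over runs) 75% times in minutes, 72-hour rule vs last-reading censoring, with the shift.

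| n per arm | m = 1 | m = 2 |
|---|---|---|
| 8 | 133 vs 133 (0) | 181 vs 137 (44) |
| 9 | 144 vs 134 (10) | 192 vs 143 (49) |
| 10 | 152 vs 127 (25) | 203 vs 140 (63) |
| 11 | 159 vs 131 (28) | 212 vs 133 (79) |
| 12 | 134 vs 134 (0) | 155 vs 134 (21) |
| 13 | 139 vs 134 (5) | 166 vs 139 (27) |
| 14 | 144 vs 128 (16) | 169 vs 138 (31) |
| 15 | 148 vs 131 (17) | 175 vs 132 (43) |
| 16 | 133 vs 133 (0) | 150 vs 135 (15) |
| 17 | 136 vs 132 (4) | 153 vs 135 (18) |

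Repeat runs differ by a few minutes: at n = 11 the shifts came out at 25 to 28 (m = 1) and 76 to 79 (m = 2). Eleven per arm is the most sensitive size. The 75% point needs 9 of 11 events, and two event-free subjects leave exactly 9.

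**The case against.** The strongest objection is that nothing visible shows any subject without a recorded value ≤ 38°C, or any readings that stopped early. A reader might infer from the rule that the reported times are overstated. The documents do not support that, because the effect is zero if every subject crossed or if readings continued past about 200 minutes. This objection stands, and the point is conditional.

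A reader might also combine the Synopsis with section 9.7.1.7 and infer that completers discharged early were carried to 72 hours, distorting the results. A disposition list is not a censoring definition. More importantly, a discharge at 10, 24 or 48 hours cannot move percentiles reached by 195 minutes, wherever the subject is censored. Where consent was refused, testing stopped at withdrawal, so discontinuation is then close to the last possible reading.

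A third tempting reading is that the rule explains the 70-minute gap. That needs about two affected subjects, all in the SOC-only arm, at an arm size near the most sensitive one. None of this is documented.

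Nor does the interpolation of cooling rate ("using straight-line interpolation for non-monotonically missing data points only") show that crossing times are wrongly dated. The endpoint is the first observed reading ≤ 38°C, so dating it to that reading follows the definition, and only an undocumented imbalance in gaps between arms would bias the comparison.

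Finally, much of the secondary and exploratory text (sections 9.7.1.9.3 and 9.7.1.9.4) is redacted and may define censoring for this endpoint. The ITT result is reported as similar, and the overall efficacy conclusion rests on neurological function. These facts limit the consequence. They do not make the visible rule the right one for an event seen only at readings.

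**Conclusion.** The concern holds in conditional form. As written, the rule counts unmeasured time as event-free, and relative to last-reading censoring it can only lengthen the time to ≤ 38°C. Whether it altered the reported 90.0 vs 103.0 and 125.0 vs 195.0 minutes cannot be told from the documents.

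Its size for an arm's 75% time is zero with no affected subject, 0 to about 28 minutes with one and about 15 to 79 with two. These figures rest on assumed lognormal times, 8 to 17 subjects per arm, Kaplan-Meier estimation and readings that stop before the subject's own crossing. They are not estimates of the bias in this trial. Severity is minor: a non-primary endpoint, with p-values declared exploratory.

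**What to change.** Replace the censoring sentence in section 9.7.1.4 with: *Subjects without the event are censored at their last assessment of that outcome (for time to ≤ 38°C, the last rectal temperature), at the latest 72 hours.* This also removes the question of whether early discharge counts as discontinuation.

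Then re-run time to ≤ 38°C in the ITT and mITT sets, report the number censored per arm with their last-reading times, and correct the median and 75% times if they change. If no subject was event-free, or all event-free subjects were read past about 200 minutes, a sentence saying so confirms the reported percentiles.

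The cost is one sentence, one changed censoring date in the program and a re-run, with no new data. The downside is that the 75% contrast may become less favourable and less precise. Last-reading censoring also assumes that subjects whose readings stopped would have cooled like those still being read, which the listed last-reading times help the reader to judge.
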